01.24.2017

**THE CLINICAL EFFECTS OF EXERCISE PROGRAM ADDED
TO PULMONARY REHABILITATION PROGRAM IN PATIENTS
WITH CYSTIC FIBROSIS**

NCT Number: 03295201

This study was planned to be a prospective single-blinded randomized controlled study and was performed between March 2017 and October 2017. Local ethics committee approval was taken (Marmara University, Istanbul, Turkey). Informed consents were obtained from the families of children. The inclusion and exclusion criteria were determined as shown below:

Inclusion Criteria

1. Patients diagnosed with cystic fibrosis (CF)
2. Patients aged between 6-14
3. FEV1 greater than 30%

Exclusion Criteria

1. Presence of cor pulmonale
2. Spinal fracture story
3. Currently under IV medication
4. Severe gastroesophageal reflux

The patients were equally randomized into two groups according to the closed envelope system. One group planned to treat six weeks with pulmonary rehabilitation and postural exercise program (Group 1), while other group being treated with pulmonary rehabilitation program alone (Group 2). Patients were assessed for respiratory function with FEV1, pain level with Visual Analog Scale (VAS), quality of life with The Cystic Fibrosis Questionnaire-Revised Child Version (CFQR), exercise tolerance with Modified Shuttle Test (MST) and postural stability with Neurocom Balance Master® Device Limits of Stability Test (LOS). All tests were performed before treatment and six weeks, three months and six months after treatment. Cobb and Modifiye Cobb angles were measured on radiographic examinations to evaluate spinal deformities before and six months after treatment.

Treatment:

Pulmonary Rehabilitation

Active cycle of breathing techniques (ACBT) was preferred for pulmonary rehabilitation. ACBT was applied by a therapist once per a week for six weeks. A daily schedule was given for the other days of the week to ensure permanence of treatment. ACBT is a commonly used chest physiotherapy method for secretion removal from lungs. Each ACBT cycle consists a sequence of breathing control, thoracic expansion exercises and forced expiration technique. These cycles are performed consecutively until the secretion is completely discharged.

Postural exercise Program

Thoracic vertebra mobilization, pectoral stretching, scapula and thoracic extensors strengthening and core stability exercises were applied by a therapist once per a week for six weeks. A daily schedule was given for the other days of the week to ensure permanence of treatment.

Assessment:

The Cystic Fibrosis Questionnaire-Revised (CFQR)

The Cystic Fibrosis Questionnaire-Revised is the most commonly used quality of life measurement tool in patients with CF and is found to be valid and reliable in Turkish. The child version of this test consists 35 questions about physical function, emotional function, social function, body appearance, eating disorders, treatment difficulties, respiratory and digestive symptoms. Total score is calculated between 0-100 and higher scores define better condition.

Modified Shuttle Test (MST)

The Modified Shuttle Test is an easy test that can show exercise tolerance and cardiorespiratory status in children with CF. The patient is asked to walk until feeling tired between two fixed objects with a 10-meter interval, starting at normal walking speed and increasing the speed at the beginning of each minute. Maximum distance is measured for the test.

Limits of Stability Test (LOS)

The Limits of Stability Test consists a 18x60 inch of a pressure platform which connected to a computer system. The patient is asked to stand on the platform barefoot and watch the image which can be moved by trunk movement on the computer the monitor. It is required to move the image towards to target points on monitor with commands. Reaction time, movement velocity, endpoint excursion, maximum excursion and direction control parameters are calculated during these trunk movements.

Radiographic evaluation

The Cobb angle was measured on antero-posterior scoliosis graphs by the angle between the superior end plate of the vertebra corpus where the curve begins and the end plate of the vertebra corpus which the curve ends. The Modified Cobb angle was found on lateral scoliosis graphs by the angle between the superior end plate of the T4 vertebra corpus and the inferior end plate of the T12 vertebra corpus.

Statistical analysis

Statistical analysis of the study was calculated using the SPSS for Windows 20.0 program. Normal distribution of quantitative values was assessed by histogram, Q-Q graph and normality tests. The Mann-Whitney U test was used to compare the measurement values between the two groups, and the Friedman test was used to compare the intra-group parameters. A statistical significance level of $p < 0,05$ was accepted. The Wilcoxon test was used to compare pre-treatment and post-treatment 6th-week, 3rd-month and 6th-month values separately. Bonferroni correction was considered $p < 0,017$ statistically significant for evaluating the results. A Spearman and Pearson correlation analysis was performed to examine the relationship between the radiographic values measured by two different clinicians. The intraclass correlation coefficient for the interobserver reliability analysis was calculated for radiographic measurements.

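### The between-group test ignores the pre-treatment value collected for every outcome; it stays valid but can lose precision that the data would give

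*Combined protocol and SAP*

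**What the plan says.** Of the Combined protocol and SAP, two places matter.

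- **Statistical analysis section.** The only comparison of the two groups is "The Mann-Whitney U test was used to compare the measurement values between the two groups". The other tests of the outcomes work within groups or over time: "the Friedman test was used to compare the intra-group parameters", and "The Wilcoxon test was used to compare pre-treatment and post-treatment 6th-week, 3rd-month and 6th-month values separately". The pre-treatment value is named only in that last sentence, which does not compare the groups. The section names no covariate, ANCOVA, rank ANCOVA, mixed model or between-group change score.
- **Opening study description.** For FEV1, VAS, CFQR, MST and LOS, "All tests were performed before treatment and six weeks, three months and six months after treatment". For the radiographs, "Cobb and Modifiye Cobb angles were measured on radiographic examinations to evaluate spinal deformities before and six months after treatment". Every outcome therefore has a baseline. Allocation was random and equal: "The patients were equally randomized into two groups according to the closed envelope system".

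**The concern.** The trial asks whether adding postural exercise to pulmonary rehabilitation helps, and only the between-group comparison answers that. As written, it makes no stated use of baseline. Two things follow.

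1. **Precision.** Where baseline predicts follow-up, part of the follow-up variance can be explained. An unadjusted test leaves it in as noise.
2. **Chance imbalance.** If the groups differ at baseline by d SD, the expected follow-up difference moves by about rho × d, where rho is the baseline–follow-up correlation. The imbalance is observed, but the planned test cannot take account of it.

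The wording also leaves open whether change from baseline was meant. Change scores use baseline, but with a fixed coefficient of one, which is not the same as adjusting for it.

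**Working it through.** **The plan's own figure.** The only derived number in the section is the Bonferroni threshold for three pre/post comparisons: 0.05/3 = 0.0167, which rounds to the stated 0.017. No sample size, power, SD, effect size or correlation is given, so no power figure can be reproduced.

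**Inputs.** From the documents: equal randomisation, Mann-Whitney test, significance level 0.05, baseline available. Assumed: two-sided testing, 10–30 per group, a true effect of 0.6 SD, rho from 0 to 0.85, and normal data unless stated.

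**Step 1: theory.** Relative to an unadjusted follow-up comparison, the variance of the group difference is

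- baseline-adjusted: 1 − rho²
- change score: 2(1 − rho)

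| rho | 1 − rho² | equivalent sample-size gain, 1/(1 − rho²) | 2(1 − rho) |
|---|---|---|---|
| 0.3 | 0.91 | 1.10 | 1.40 |
| 0.5 | 0.75 | 1.33 | 1.00 |
| 0.7 | 0.51 | 1.96 | 0.60 |
| 0.8 | 0.36 | 2.78 | 0.40 |

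The difference 2(1 − rho) − (1 − rho²) equals (1 − rho)², which is never negative. In theory, change scores therefore never beat ANCOVA, and below rho = 0.5 they are worse than using follow-up values alone.

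**Step 2: simulated power.** 20,000 trials per cell, effect 0.6 SD, 20 per group:

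| rho | Mann-Whitney, follow-up | Mann-Whitney, change | rank ANCOVA | ANCOVA |
|---|---|---|---|---|
| 0 | 0.430–0.444 at every rho | 0.244 | 0.428 | 0.443 |
| 0.3 | | 0.332 | 0.455 | 0.478 |
| 0.5 | | 0.435 | 0.524 | 0.556 |
| 0.7 | | 0.650 | 0.674 | 0.726 |
| 0.85 | | 0.908 | 0.886 | 0.935 |

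Other group sizes, rho in the same order:

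- 10 per group: Mann-Whitney on follow-up 0.213–0.221; rank ANCOVA 0.227/0.247/0.272/0.357/0.541; ANCOVA 0.233/0.257/0.294/0.406/0.654.
- 30 per group: Mann-Whitney on follow-up 0.598–0.604; rank ANCOVA 0.606/0.636/0.714/0.850/0.977; ANCOVA 0.620/0.665/0.749/0.887/0.992.

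A second simulation with other assumptions (15 per group, 0.8 SD, 2,000 trials per setting) shows the same pattern. Mann-Whitney on follow-up has 53–54% power, against 58/65/78/90% for rank ANCOVA at rho 0.3/0.5/0.7/0.8.

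**Step 3: type I error.** With no true effect, over all group sizes in the main simulation: Mann-Whitney 0.041–0.052, rank ANCOVA 0.047–0.053, ANCOVA 0.048–0.053. The planned test is valid.

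**Step 4: error given the baseline gap that occurs.** At 20 per group, one SE of the baseline difference is √(2/20) = 0.316 SD. A gap of that size shifts the follow-up difference by rho × 0.316 = 0/0.09/0.16/0.22/0.27 SD. With no true effect:

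- Gap of 1.7–2.3 SE (about 7% of trials): Mann-Whitney rejects in 0.052/0.085/0.118/0.194/0.251, ANCOVA in 0.053/0.052/0.047/0.055/0.046.
- Gap of 0.9–1.1 SE: Mann-Whitney rejects in 0.056/0.049/0.048/0.046/0.022, so the rate is not raised.

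**Step 5: skewed data.** Log-normal outcome (log-SD 0.75, rho on the log scale), 20 per group: Mann-Whitney 0.80; rank ANCOVA 0.796/0.822/0.872/0.951/0.994; ANCOVA 0.530/0.560/0.614/0.743/0.899. Here ANCOVA loses to the planned test up to rho 0.7, and rank ANCOVA does not.

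**The case against.** The strongest reply is that nothing here is an error. An unadjusted rank test in a randomised trial is legitimate and holds its type I error. That stands, and the point is one of efficiency only.

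Further objections, and what remains of each:

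- **The loss cannot be sized from the documents.** True. At rho 0.3 and 20 per group, rank ANCOVA gains about 2 points and ANCOVA about 4. Only rho of about 0.7 or more gives a large gain, and the documents support no particular value. But the gain is essentially never negative for rank ANCOVA, and the baselines are already collected.
- **Change may have been meant.** If so, little is lost at high rho. At rho 0.85 the Mann-Whitney test on change (91%) even slightly beats rank ANCOVA (89%), though not ANCOVA (94%). The loss then sits at low rho: 24% against 44% for ANCOVA at rho 0. The wording needs settling either way.
- **The conditional error rates describe a selected subset.** They do, and lower rates elsewhere offset them. They show what an observed imbalance does to interpretation, not a failure of overall error control.
- **Parametric ANCOVA suits skewed or bounded outcomes poorly.** This has force. With an integer scale and about half the values at the floor (20 per group), ANCOVA moves power only from 30% to 32% at rho 0.5 and to 40% at rho 0.7. At 10 per group it is at or below Mann-Whitney for rho up to 0.5 (13% against 16% at rho 0). Rank ANCOVA must therefore be the named test for such outcomes.
- **The study is over.** The description says it "was performed between March 2017 and October 2017". This limits the standing of a new analysis but does not prevent one.

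**Conclusion.** The concern holds. No baseline-adjusted between-group comparison is specified, although every outcome has a pre-treatment value. The planned test is valid, and the fault is avoidable loss of precision. At 20 per group and 0.6 SD with normal data, ANCOVA gains nothing at rho 0, about 12 points at rho 0.5 and about 50 points at rho 0.85 over the planned test on follow-up values. Group size, effect, correlation and distribution are all assumed, because the documents give none of them. The direction of the result is firm and its size is not. The plan should be changed, but results from the planned test are not invalidated by this point.

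**What to change.** 1. State whether the group comparison is of follow-up values or of changes.
2. Make the comparison baseline-adjusted for each outcome at each post-treatment visit, and at six months only for the Cobb and Modified Cobb angles.
3. Fix the method in advance, not after a normality check. Use ANCOVA on the outcome's own baseline, reporting the adjusted difference with its 95% CI, with rank ANCOVA as the sensitivity analysis.
4. For any outcome expected beforehand to be strongly skewed or to pile up at a bound (VAS is a candidate), name rank ANCOVA as the main test.
5. A mixed model over visits is optional. If used, apply a small-sample degrees-of-freedom correction.
6. If the data have already been analysed, label the adjusted analysis post hoc.

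**Cost.** No new data: only revised SAP wording, slightly more analysis work and one degree of freedom per comparison. The main risk is lower power if ANCOVA is applied to a strongly skewed outcome, which item 4 guards against.

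### The planned tests use only complete or attending children, so the within-group Friedman test loses power and the six-month group comparison ignores earlier data and could be biased by unequal, outcome-related loss

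*Combined protocol and SAP*

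**What the plan says.** The study description sets the schedule: "All tests were performed before treatment and six weeks, three months and six months after treatment". Radiographs are the exception, taken before treatment and at six months only. Allocation is 1:1: "The patients were equally randomized into two groups according to the closed envelope system".

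The Statistical analysis section gives three tests for these data:

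- Between groups: "The Mann-Whitney U test was used to compare the measurement values between the two groups".
- Within each group, across visits: "the Friedman test was used to compare the intra-group parameters".
- Within each group, baseline against each follow-up visit: "The Wilcoxon test was used to compare pre-treatment and post-treatment 6th-week, 3rd-month and 6th-month values separately".

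The general threshold is "A statistical significance level of $p < 0,05$ was accepted", with a stricter one for the multiple comparisons: "Bonferroni correction was considered $p < 0,017$ statistically significant for evaluating the results".

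The documents give no sample size, expected attrition or rule for a missed visit. They do not say that children are analysed in their allocated group. No named method uses the data of a child with some visits missing, and the SPSS missing-value setting is not given.

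**The concern.** Each test decides for itself who is analysed. Friedman needs a value at every visit, so one missed visit removes the child and discards the values that were collected. Wilcoxon needs baseline and the one follow-up visit. Mann-Whitney needs only the visit being compared. Followed exactly, the plan gives a completers' analysis within groups and an attenders' analysis between groups.

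The between-group result matters most, because it alone estimates the randomised effect. A child seen at baseline, six weeks and three months but not at six months contributes nothing to the six-month comparison. If children doing poorly leave one group more than the other, the attenders are no longer comparable. Group 1 alone carries the added weekly and daily exercise, so unequal loss is plausible. If Group 1's losses are its poorer performers, the added program looks better than it is.

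Some missed visits are foreseeable with long follow-up in children with a chronic disease. The calendar is also tight. The study "was performed between March 2017 and October 2017", at most about 244 days. Six weeks of treatment plus six months takes about 225 days, leaving about 19 days for enrolment, or about 61 if six months is counted from baseline.

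**Working it through.** **The plan's own figure.** The only derived number is the corrected threshold: 0.05/3 = 0.0167, which rounds to 0.017. Nothing below depends on it. There is no design power or attrition figure to reproduce, so all remaining inputs are assumptions.

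**Children kept.** Let m be the chance of missing each follow-up visit, independently, with baseline complete. Friedman keeps (1−m)³, a single Wilcoxon pair or Mann-Whitney visit keeps 1−m, and a model needing baseline and at least one follow-up visit keeps 1−m³.

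| m | Friedman keeps | Friedman loses | One visit or pair keeps | Longitudinal model keeps |
|---|---|---|---|---|
| 5% | 85.7% | 14.3% | 95% | over 99.9% |
| 10% | 72.9% | 27.1% | 90% | 99.9% |
| 15% | 61.4% | 38.6% | 85% | 99.7% |

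**Friedman power.** Simulated with 20 per group, correlation 0.7 between visits and shifts of 0.4, 0.3 and 0.3 SD at the three follow-up visits, power falls from 39% with full data to 31%, 28% and 23% at m = 5%, 10% and 15%.

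**Six-month Mann-Whitney with no true effect.** Tests are two-sided at 0.05 (the plan does not state sidedness). Bias is Group 1 minus Group 2 in SD units, higher being better. The last three rows assume correlation 0.7, about 24% loss in Group 1 depending on the week-6 value, and 20% random loss in Group 2.

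| Loss pattern | Bias (SD) | False-positive rate |
|---|---|---|
| 20% random, both groups | about 0 | 4.6–5.1% |
| Outcome-related, same pattern in both groups | about 0 | about 4.2% |
| Group 1 only: 40% loss if the three-month value is below the mean; correlation 0.6; Group 2 complete | 0.12 | 5.7–6.4% |
| Group 1 loss 33% at −1 SD, 15% at +1 SD | 0.08 | not needed for the range |
| Group 1 loss 41% at −1 SD, 8% at +1 SD | 0.14 | about 6–7% |
| Very strong: Group 1 loss above 53% at −1 SD, almost none at +1 SD | 0.25 | 8%, 9%, 12% at 15, 20, 30 per group |

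Two of these can be checked by hand.

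- The 0.12 SD row: the mean of the lower or upper half of a standard normal is ∓0.798. Retained children are 0.5 from the upper half and 0.3 from the lower, so their mean three-month value is (0.5 × 0.798 − 0.3 × 0.798)/0.8 = 0.20 SD. Multiplying by the correlation, 0.6 × 0.20 = 0.12 SD.
- The ceiling: if exactly the lowest 24% of Group 1 at week 6 all left, the six-month shift would be 0.7 × 0.311/0.76 = 0.29 SD, where 0.311 is the normal density at the 24% point. The 0.25 SD row is therefore near the worst case.

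**What earlier data recover.** When loss depends on the observed week-6 value, a regression using baseline and week 6 has bias within about 0.01 SD. When loss depends on the unseen six-month state, the same regression keeps about 0.05 to 0.20 SD, roughly half the bias.

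**Baseline adjustment without any missing data.** With correlation 0.7, adjustment cuts the residual SD to √(1 − 0.49) = 0.71, so a 0.7 SD effect becomes 0.7/0.71 = 0.98 residual SD. At 15 per group, simulated power rises from about 44% for Mann-Whitney on six-month values to about 70%.

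**The case against.** The strongest reply is that no missed visit is documented and that the study description reports the tests as done at all four times. That sentence describes the schedule and does not establish that every child attended, but it does mean that attrition, its mechanism and the sample size are all assumed here. Nobody can say from the documents that a bias occurred.

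Two stronger readings are tempting and do not hold. A reader might infer that Friedman's deletion distorts the six-month group comparison. It cannot, because Friedman is applied only within groups and the group comparison is a separate Mann-Whitney test. A reader might also infer that the three tests always rest on different children. They can, but need not. With baseline complete, the six-month Wilcoxon and Mann-Whitney tests use the same children. If six months is the only visit missed, Friedman uses them too, and a listwise setting would equalise all three.

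It is also fair to say that lost Friedman power matters less, since that test does not estimate the randomised effect, and that rank tests are a defensible choice for a skewed scale such as VAS. Both points stand. They limit the Friedman part and explain why a rank test should remain. They do not answer the omission of baseline and earlier visits from the between-group comparison. Finally, the mixed model recommended below was not itself simulated: the figures for recovered bias and power come from regressions on earlier values.

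**Conclusion.** The point holds in a limited form. As written, the plan yields a complete-case within-group analysis that loses power, and an available-case six-month comparison that leaves out baseline and earlier follow-up.

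Bias in that comparison requires loss that is related to outcome and differs between groups. Under the assumed one-sided patterns it is roughly 0.1 to 0.25 SD in favour of the added program, with a false-positive rate of about 6% to 12%. The upper end needs very strong dependence of dropout on outcome. Random loss, or the same pattern in both groups, gives essentially none.

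A reader might take the near-zero bias of an estimate using earlier visits as a guarantee. It holds only where missingness depends on observed values; otherwise the bias is reduced but not removed. Because baseline adjustment improves the group comparison even with complete data, the change is worth making whatever the attrition proves to be.

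**What to change.** For each outcome measured at four visits, make the main group comparison a linear mixed model for the follow-up values. Use all available visits of all randomised children, analysed as allocated, with group, visit, group-by-visit and the baseline value, and report the group difference with its confidence interval at each visit. Keep Mann-Whitney on change from baseline as a sensitivity analysis, chiefly for skewed outcomes such as VAS, and label Friedman and Wilcoxon as descriptive. Report how many children in each group contribute at each visit and why visits were missed. The radiographic angles, measured twice, fall outside this model.

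The cost is analysis wording and a little programming, with no new data. The downside is reliance on roughly normal residuals in what may be a small sample, which the rank-based sensitivity analysis addresses in part.

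### The randomised Group 1 versus Group 2 comparison is planned but not made decisive, while about two thirds of the planned tests are before-after tests that cannot isolate the postural programme

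*Combined protocol and SAP*

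**What the plan says.** The title asks about the effect of exercise added to pulmonary rehabilitation. The opening study description sets out two randomised arms. The experimental arm is given as "One group planned to treat six weeks with pulmonary rehabilitation and postural exercise program (Group 1"). The comparator receives the shared component only, and its description reads "while other group being treated with pulmonary rehabilitation program alone (Group 2"). Allocation is equal: "The patients were equally randomized into two groups according to the closed envelope system". Under Treatment, the rehabilitation component is the active cycle of breathing techniques (ACBT), so ACBT is common to both arms.

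On timing, "All tests were performed before treatment and six weeks, three months and six months after treatment". The spinal angles are measured only twice: "Cobb and Modifiye Cobb angles were measured on radiographic examinations to evaluate spinal deformities before and six months after treatment". Under Inclusion Criteria the population is "Patients aged between 6-14".

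The Statistical analysis section names one between-group method, the Mann-Whitney U test on the measurement values. It does not say whether these are changes from baseline. It names two within-group methods. For the first, "the Friedman test was used to compare the intra-group parameters", and a significance level of 0.05 follows. For the second, "The Wilcoxon test was used to compare pre-treatment and post-treatment 6th-week, 3rd-month and 6th-month values separately", and a Bonferroni threshold of p < 0.017 follows as the rule for judging results. The section does not say which of these comparisons decides whether the postural programme works.

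**The concern.** ACBT, the passage of time and repeated testing act on both arms. A before-after change in Group 1 is therefore the sum of the postural effect and everything the arms share. The shared part includes practice on the Modified Shuttle Test (MST) and the Limits of Stability test (LOS), each done up to four times. It also includes about six months of growth for measures that are not scaled for it. The Bonferroni correction limits chance findings among the three visits. It does nothing about a real change that has another cause.

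The plan gives the before-after tests a formal significance rule and does not limit what may be concluded from them. That leaves open two unsound readings: taking a significant change in Group 1 as evidence for the postural programme, and taking significance in one arm but not the other as a difference between arms. The second pattern can arise by chance when the arms change by the same amount.

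**Working it through.** **The plan's own figure.** Three before-after comparisons per outcome give 0.05/3 = 0.01667, which rounds to the stated 0.017. The threshold therefore fits the three Wilcoxon tests. The Mann-Whitney and Friedman tests fall under the general 0.05.

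**How many tests are within-group.** The four-visit outcomes are FEV1, pain VAS, CFQR total, MST distance and five LOS parameters, nine in all. Two spinal angles have two visits each.

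- Within-group, per four-visit outcome: 2 Friedman + 2 × 3 Wilcoxon = 8.
- Between-group, per four-visit outcome: 3 Mann-Whitney tests after baseline, or 4 if baseline is tested too.
- Each angle adds 2 within-group tests (one per arm) and 1 or 2 between-group tests.

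| Counting rule | Within | Between | Share within |
|---|---|---|---|
| One four-visit outcome | 8 | 3 to 4 | 8/11 = 73% to 8/12 = 67% |
| All outcomes, LOS as five | 9×8 + 2×2 = 76 | 29 to 40 | 76/105 = 72% to 76/116 = 66% |
| All outcomes, LOS as one | 5×8 + 2×2 = 44 | 17 to 24 | 44/61 = 72% to 44/68 = 65% |

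**Chance of a discordant pattern when the arms do not differ.** Suppose both arms have the same true change and the same within-arm probability p of reaching p < 0.017. The arms are independent, so

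Pr(Group 1 significant, Group 2 not) = p(1 − p).

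The mirror pattern has the same probability. Nine outcomes at three later visits make 27 pairs. If every pair had the same p, the expected number of patterns would be 27 × p(1 − p). Correlation between outcomes does not alter an expected count.

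| p | p(1 − p) | Expected among 27 |
|---|---|---|
| 0.017 (no shared change) | 0.0167 | 0.45 |
| 0.2 or 0.8 | 0.16 | 4.3 |
| 0.3 or 0.7 | 0.21 | 5.7 |
| 0.5 | 0.25 | 6.75 |
| 0.95 | 0.0475 | 1.3 |

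Where the change is a worsening, such a pattern would not favour Group 1.

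**Simulation.** There was no postural effect and both arms had the same change, with 2,000 trials per setting. The inputs are assumptions that the documents do not give: normal data, correlation 0.7 between visits, 10, 15 or 20 patients per arm, and a shared change of 0.3, 0.5 or 0.8 SD.

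- The Group 1 Wilcoxon test at 6 months was significant at 0.017 in 6% to 96% of trials.
- Significance in Group 1 but not Group 2 occurred at 6 months in about 4% to 24%, and at one or more visits in about 10% to 49%.
- The Mann-Whitney test at 6 months was significant at 0.05 in about 4% to 6%, on values or on change from baseline. At one or more of the three visits, uncorrected and on values, it was significant in about 10% to 12%.
- With no shared change, the discordant pattern at 6 months occurred in 1.4% to 2.2%.

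At a single visit the between-group test holds its error rate whatever the shared change. The before-after tests respond to the shared change itself.

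**The case against.** The strongest reply is that the right test is already in the plan. Mann-Whitney between the randomised groups is named first and has its own 0.05 rule, and in it the shared influences cancel on average. That stands. The fault is that this test is not made decisive, not that it is missing.

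Four stronger readings are tempting, and the documents do not support them.

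- *The trial lacks an untreated arm.* For an add-on question, rehabilitation alone is the right comparator. The absence matters only if a within-group change is read as a treatment effect.
- *The plan will declare benefit because one arm reached significance and the other did not.* The Statistical analysis section lists tests. It never says that within-group p-values will be compared across arms or will override Mann-Whitney. It is silent, and that silence is the whole of the criticism.
- *The 0.017 threshold gives the before-after tests higher standing.* It makes them stricter, as an ordinary follow-up to Friedman, and a count of tests does not show their weight.
- *Growth affects every outcome.* The FEV1 inclusion criterion is a percentage, which suggests percent predicted and hence some adjustment for growth. Nothing links VAS or CFQR to growth. MST distance is the clearer case.

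It is also fair to object that 4.3 to 6.8 patterns among 27 needs a shared change in every outcome at every visit and a detection chance of 0.2 to 0.8. The documents establish neither.

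**Conclusion.** The point holds in a limited form. The title question can be answered only by Group 1 versus Group 2. The plan includes that comparison but does not say that conclusions about the postural programme rest on it, although 65% to 72% of the planned tests over all outcomes are within-group. A before-after change in Group 1 cannot separate the postural programme from what both arms share.

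The size is conditional. If the arms change equally, the chance of significance in Group 1 alone runs from about 2% per pair with no shared change to 25% at p = 0.5, and falls again as p nears 1. That is about 0.45 to 6.8 expected patterns over 27 pairs, with as many expected in the mirror direction. Without a sample size, SD or expected change, this is a range under assumptions and not a forecast. Confidence is high about the silence in the plan. The documents give no basis for predicting how the results will be reported. This is a cheap improvement.

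**What to change.** Add to the Statistical analysis section, and follow in the report:

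1. Conclusions about the effect of the postural programme rest only on the Group 1 versus Group 2 comparison.
2. That comparison is made on change from baseline or adjusted for baseline, and is reported as a between-group difference with its confidence interval. If Mann-Whitney is kept, the Hodges-Lehmann estimate and its interval would serve.
3. Friedman and Wilcoxon results are labelled as descriptive change within each arm. They are not used to say that either treatment works, and the arms are not compared by which one reached p < 0.017.

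The cost is wording and some re-analysis of data already planned for collection. No new data and no additional arm are needed. The downside is that within-group p-values can no longer be quoted as evidence of efficacy.
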